2.3.1 Efficacy populations

The primary efficacy analysis population will be the ITT population.

2.3.1.1 Intent-to-treat population

The intent-to-treat population includes all randomized patients who received at least one dose of IMP, irrespective of the treatment actually being received, analyzed according to the treatment group allocated by randomization.

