# 8.4 BLINDING PROCEDURES

As Toujeo and the control drug Tresiba are distinguishable, this study is an open-label design, and no attempt will be made to blind administration.

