#### **IVRS/IWRS contact**

After the baseline assessments are completed and eligibility confirmed, the investigator contacts IVRS/IWRS for randomization. The treatment group (ie, the Toujeo or Tresiba) is notified by IVRS/IWRS.

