# 11.3 ANALYSIS POPULATIONS

#### **11.3.1 Efficacy populations**

#### 11.3.1.1 Intent-to-treat population

The primary efficacy population will be the ITT population, which includes all randomized patients who received at least one dose of IMP, irrespective of the treatment actually being received, analyzed according to the treatment group allocated by randomization.

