2.1.3 Efficacy endpoints

The baseline value for efficacy endpoints is the last available value prior to the first injection of open-label IMP.

HbA1c and FPG are measured at a central laboratory, for scheduled (see study flowchart in Table 1) and unscheduled time points.

Patients measure their SMPG using the blood glucometer and document them into the diary. The following SMPG values are copied in the eCRF (see study flowchart in Table 1).

In case of premature and permanent IMP discontinuation, patients should have a visit as soon as possible with the assessments normally planned in Visit 20 (Week 24). Afterward, the patients should continue in the study up to the scheduled date of study completion. They should be followed up according to the study procedures as specified in the protocol (except for the 7-day safety post-treatment follow-up).

In case of premature permanent IMP discontinuation or rescue therapy intake, the process described in Section 2.5.4 will be applied to retrieve efficacy assessments performed at the end of treatment visit or at pre-rescue visit.

Observation period of efficacy endpoints

- The 24-week on-treatment period (used to assess the on-treatment estimand) for efficacy endpoints (primary and secondary efficacy endpoints) is defined as the time from the first injection dose of open-label IMP up to:
 - 7 days after date of last IMP administration for HbA1c, or up to the introduction of the rescue therapy, whichever is earlier for the patient,
 - 0 day after date of last IMP administration for 4-point and 8-point SMPG and insulin dose, or up to the introduction of the rescue therapy, whichever is earlier for the patient,
 - 1 day after date of last IMP administration for FPG and fasting SMPG, or up to the introduction of the rescue therapy, whichever is earlier for the patient,
 - 2 days after date of last IMP administration for hypoglycemia or up to the introduction of rescue therapy, whichever is earlier for the patient,
- **The randomized 24–week period** (used to assess the intent-to-treat [ITT] estimand) for efficacy variables is defined from first dose of IMP up to Week 24, (visit 20), regardless of study treatment discontinuation and intake of rescue therapy.

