2.3 ANALYSIS POPULATIONS

Patients treated without being randomized will not be considered randomized and will not be included in any efficacy population.

Patients who are dispensed study drug without calling the IVRS or before calling the IVRS are considered non-randomized patients. They are excluded from any population for analysis,

including safety. However, if these patients experienced any significant safety event, they should be documented separately in the clinical study report.

The randomized population includes any patient who has been allocated to a randomized treatment regardless of whether the treatment kit was used.

For any patient randomized more than once, only the data associated with the first randomization will be used in any analysis population. The safety experience associated with any later randomization will be assessed separately.

The safety experience of patients treated and not randomized will be reported separately, and these patients will not be in the safety population.

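### The population called ITT is a modified ITT set: it drops randomized patients who never inject, in an open-label trial where the arm is known before the first dose

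*SAP*

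**What the plan says.** Protocol 11.3.1.1 and SAP 2.3.1.1 agree. The SAP says "The intent-to-treat population includes all randomized patients who received at least one dose of IMP". The protocol's efficacy set is "all randomized patients who received at least one dose of IMP, irrespective of the treatment actually being received", analysed by allocated arm. SAP 2.3 also defines a wider set: "The randomized population includes any patient who has been allocated to a randomized treatment regardless of whether the treatment kit was used". That wider set serves disposition, baseline and medication tables. No efficacy analysis uses it.

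On masking, Protocol 8.4 says "this study is an open-label design, and no attempt will be made to blind administration". At the baseline visit (Protocol 10.1.2.1), once eligibility is confirmed, "The treatment group (ie, the Toujeo or Tresiba) is notified by IVRS/IWRS". Pen training and dispensing follow. That visit takes place in the morning, and Protocol 8.2.3 sets self-injection between 6 and 8 PM.

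SAP 2.1.3 links the randomized 24-week period to the ITT estimand, but the period "for efficacy variables is defined from first dose of IMP up to Week 24". The penalized imputation and tipping-point analyses (SAP 2.4.4.1.4) and the responder endpoints (SAP 2.4.4.2.1) all use the ITT population. For the responder endpoints, missing HbA1c counts as failure.

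**The concern.** A one-dose requirement does little harm when the decision to start cannot be influenced by knowledge of the arm. Here patient and investigator both know the arm before the first dose. Protocol 8.4 itself says the arms can be told apart by initial dose, and Protocol section 4 lists fear of needles and worry about side effects as barriers to starting insulin. A patient who declines after learning the allocation is therefore a plausible case, and the decision could differ by arm.

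The rule also treats similar patients differently. Someone who injects once and then leaves is a responder failure and has a Week 24 value imputed, with the 0.3% penalty if in the Toujeo arm. Someone who declines the same insulin before the first injection is in neither analysis. The label ITT estimand then suggests a comparison of all randomized patients that the analysis does not deliver.

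**Working it through.** **1. The plan's own figure.** Inputs from Protocol 11.1 and SAP 1.3: margin 0.3%, SD 1.4%, true difference 0, one-sided 2.5%, power at least 90%, 460 randomized per arm.

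- n per arm = 2 × (1.960 + 1.282)² × 1.4² / 0.3² = 458 by the normal approximation (459 with the noncentral t). The stated 460 reproduces, with power 90.1%.
- SE = 1.4 × √(2/460) = 0.0923. The 95% CI half-width is 1.96 × 0.0923 = 0.181, which leaves 0.3 − 0.181 = 0.119 below the margin when the true difference is zero.

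The 460 counts randomized patients, so an all-randomized analysis matches the basis of the calculation. Power is not the issue: losing 2% of both arms would lower it only from 90.1% to 89.6%.

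**2. Which analyses change if never-dosed patients are included.**

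| Analysis | Effect |
|---|---|
| Primary MMRM, on-treatment period (SAP 2.4.4.1.1) | None; they have no on-treatment data |
| MMRM on the randomized period (SAP 2.4.4.1.3) | None, unless they have post-baseline HbA1c; an MMRM neither imputes nor counts failures |
| Penalized multiple imputation (SAP 2.4.4.1.4) | Week 24 imputed, plus 0.3% in the Toujeo arm |
| Tipping point (SAP 2.4.4.1.4) | Imputed, then shifted by δ |
| HbA1c-target responders, with or without hypoglycemia (SAP 2.4.4.2.1) | Counted as failures |

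**3. Responder size.** Neither document gives a number of never-dosed patients, so k is an assumption, as is 50% responders among the treated. With 460 randomized in the arm, the rate is 50% in the one-dose set and 50% × (460 − k)/460 in the all-randomized set. The change is −50 × k/460 points:

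- k = 2: −0.2 points
- k = 5: −0.5 points
- k = 10: −1.1 points
- 10 in one arm and 2 in the other: the difference between arms moves by 50 × 8/460 = 0.9 points

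**4. HbA1c size.** If k patients would do D worse than the rest of their arm, the arm mean moves by k × D/460.

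- k = 10, D = 1%: 10/460 = 0.02%
- The plan's own 0.3% penalty on 10 Toujeo patients: 10 × 0.3/460 = 0.007%
- To use up the 0.119, the share of one arm lost would have to be 0.119/1.0 = 11.9% at D = 1%, or 0.119/1.5 = 7.9% at D = 1.5%

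**5. What the SAP already has.** SAP 2.1.1 gives a baseline rule for randomized, untreated patients, and the note under Table 4 in SAP 2.5.4 gives their Day 1. Missing are an efficacy period that does not begin at first dose and a statement of how their missing HbA1c is handled.

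**The case against.** The strongest reply is that no confirmatory result moves. Non-inferiority and superiority are tested only in the on-treatment MMRM, and SAP 2.4.4.4 makes the p-values for secondary endpoints descriptive. That stands. Losses would also be visible: SAP 2.2 tabulates randomized but untreated patients by arm and lists patients excluded from the ITT set. That stands too, although a count by arm does not put these patients into any efficacy estimate.

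The shifts are small under any plausible count, which is also correct. SAP 2.3.2 treats patients lost without documentation as exposed, which narrows the excluded group, but that rule is written for the safety population.

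Several stronger readings are tempting, and the documents do not support them:

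- A reader might infer that the randomized-period MMRM is distorted in the same way. It is not, unless never-dosed patients have post-baseline HbA1c. The follow-up rules in Protocol sections 9 and 10.3.4 are written for patients who discontinue the drug, and none is stated for patients who never start.
- A reader might infer that the sensitivity analyses were designed to guard against exclusions after randomization. SAP 2.4.4.1.3 and 2.4.4.1.4 speak of treatment discontinuation, rescue and missing data only.
- A reader might take the first injection to fall on the evening of Visit 2. That is an inference from the morning visit and the injection window. The order, disclosure before dose, is certain; the interval is not.
- A reader might infer that including these patients needs no new rule. The first-dose start of the period in SAP 2.1.3 says otherwise.

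**Conclusion.** The point holds as a defect of definition and labelling with a limited analytic effect. What the plan calls ITT is modified ITT, and exclusion from it can depend on the arm. The documents do not show that it did, in which direction, or for how many patients.

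The effect is confined to the penalized imputation, the tipping-point analysis and the missing-equals-failure responder endpoints. Under the assumed 2 to 10 never-dosed patients in one arm of 460, it is about 0.2 to 1.1 points in that arm's responder rate. For HbA1c it is about 0.02% if 10 such patients do 1% worse. A clear non-inferiority result would not be overturned. The change is worth making because these are the analyses where a never-starter would otherwise count against the arm, and the remedy is cheap.

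A reader might go further and infer an inflated type I error for the non-inferiority test. The documents do not support that: it would require a comparison with complete outcomes in all randomized patients, whereas the planned test uses on-treatment data to which never-dosed patients contribute nothing.

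**What to change.** - Run the penalized imputation, tipping-point and responder analyses on all randomized patients as allocated. Do the same for the ITT-estimand MMRM, using any post-baseline HbA1c that exists.
- In SAP 2.1.3, start the randomized 24-week period at randomization for untreated patients, using the baseline rule in SAP 2.1.1 and the Day 1 rule in SAP 2.5.4.
- State that their missing HbA1c is imputed in the imputation-based analyses and counted as failure in the responder analyses.
- Keep the at-least-one-dose set for the on-treatment analysis and rename it modified ITT in Protocol 11.3.1.1, the protocol synopsis and SAP 2.3.1.1.

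The cost is a small wording change in protocol and SAP and a few more patients in the sensitivity and responder tables. The downside is that responder percentages may fall slightly. The primary on-treatment analysis is unchanged.

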2.3.1.2 Per-protocol population

The per-protocol population is a subset of the ITT population with no major / critical deviations. Patients included in this population will fulfill at least the criteria below:

- Randomized and received only the treatment allocated at the randomization,
- HbA1c value at baseline,
- HbA1c value at Week 24 on treatment,
- Without initiating rescue therapy,
- Who did not permanently discontinued treatment,
- With I01 Adult patients with T2DM inadequately controlled with OADs therapy with/without GLP-1 receptor agonist at stable dose for at least 3 months,
- Without E01 HbA1c <7.5% or >10.5% (at screening),
- Without E04 Current or previous insulin use except for a maximum of 8 consecutive days or totally 15 days (eg, acute illness, surgery) during the last year prior to screening,
- Without E15 The conditions/situations may interfere the evaluation for efficacy endpoints,
- Without used prohibited medication.

2.3.2 Safety population

The safety population is defined as all randomized patients who did actually receive at least one dose of IMP, regardless of the amount of treatment administered.

In the event of patients having received treatments that differed from those assigned according to the randomization schedule, then the safety analyses will be conducted according to the treatment received rather than according to the randomization groups.

Patients will not be considered exposed if there is documented evidence that patients have not taken the study drug:

- If a patient is dispensed IMP and is lost to follow-up without any documented evidence, the patient will be considered exposed and included in the safety population,
- Randomized patients for whom it is unclear whether they took the study medication will be included in the safety population as randomized.

In addition:

- Nonrandomized but treated patients will not be part of the safety population; however, their safety data will be presented separately,
- Randomized patients for whom it is unclear whether they took the IMP will be included in the safety population as randomized,
- For patients receiving more than one study treatment during the trial, the patient will be analyzed in the treatment group in which he/she was treated longer.

2.3.3 PRO population

The analysis of PROs will be conducted on the ITT population.

2.4 STATISTICAL METHODS

2.4.1 Demographics and baseline characteristics

Parameters described in Section 2.1.1 will be summarized by treatment group and overall treatment groups using descriptive statistics.

Continuous data will be summarized using the number of available data, mean, standard deviation (SD), median, minimum and maximum for each treatment group. For insulin dose and PROs, summary statistics will include quartiles Q1, Q3 and medians. Categorical and ordinal data will be summarized using the number and percentage of patients in each treatment group.

Parameters will be summarized on the randomized population analyzed in the treatment group to which they were randomized. Similar analyses will be done on the ITT population in the as-randomized treatment group (respectively, PP population, safety population in the as-treated

treatment group) and will be included in the appendices if the size of the ITT population (respectively, PP population and safety population) is different (>10%) from the size of the randomized population for any treatment group. In the randomized population, parameters will also be summarized within each randomization stratum as per IVRS.

Medical/surgical history will be classified into primary system organ class (SOCs) and HLTs using MedDRA and will be summarized by treatment groups. Events will be sorted by SOC internationally agreed order and decreasing frequency of HLT based on incidence in the overall treatment group.

P-values on demographic and baseline characteristic data will not be calculated.

No specific description of the safety parameters will be provided at baseline. If relevant, the baseline values will be described along with each safety analysis.

No specific description of the efficacy parameters will be provided at baseline. If relevant, the baseline values will be described along with each efficacy analysis.

2.4.2 Prior or concomitant medications

The prior and concomitant medications will be presented for the randomized population.

Prior medication will be presented by treatment arm and overall whereas concomitant and post treatment medication will be presented by treatment arm.

2.4.2.1 Non-anti-diabetic medication

Non anti-diabetic medications will be summarized by treatment arm according to the WHO-DD dictionary, considering the first digit of the anatomic category (Anatomical Therapeutic Chemical [ATC]) class (anatomic category) and the first 3 digits of the ATC class (therapeutic category).

All ATC codes corresponding to a medication will be summarized, and patients will be counted once in each ATC category (anatomic or therapeutic) linked to the medication. Therefore patients may be counted several times for the same medication.

The table for non-anti-diabetic prior medications will be sorted by decreasing frequency of ATC followed by all other therapeutic classes based on the overall incidence across treatment groups. In case of equal frequency regarding ATCs (anatomic or therapeutic categories), alphabetical order will be used.

The tables for non-anti-diabetic concomitant and post treatment medications will be sorted by decreasing frequency of ATC followed by all other therapeutic classes based on the incidence in the Toujeo® group. In case of equal frequency regarding ATCs (anatomic or therapeutic categories), alphabetical order will be used.

An individual listing sorted by treatment arm and subject number will be populated instead of summary table only if few non-antidiabetic either prior or post treatment medications are observed.

2.4.2.2 Anti-diabetic medication

Antidiabetic medications will be summarized by treatment arm according to the WHO-DD dictionary considering the pharmacological class (ATC3), chemical class (ATC4) and standardized medication name.

The table for antidiabetic prior medications will be sorted by decreasing frequency of pharmacological class followed by chemical class and standardized medication name based on the overall incidence across treatment arm. In case of equal frequency, alphabetical order will be used.

The tables for antidiabetic concomitant and post treatment medications will be sorted by decreasing frequency of pharmacological class followed by chemical class and standardized medication name based on the incidence in Toujeo treatment arm. In case of equal frequency, alphabetical order will be used.

In addition, the following specific medications will be summarized:

- The anti-diabetic concomitant rescue medication will be presented by pharmacological class, chemical class and standardized medication name.
- The prohibited concomitant medication will be presented by prohibited medication category as defined in deviation and standardized medication name.

A list of ATC codes to be used in determining these medications is in Appendix B.

Prior, concomitant and post-treatment antidiabetic non-insulin therapy and rescue will also be summarized per predefined classification and standardized medication name:

- Biguanides
- SU
- Glinides
- Thiazolidinedione
- DPP-4 inhibitors
- SGLT-2 inhibitors
- GLP1-RA
- Alpha-glucosidase inhibitors
- Other.

The numbers and percentages of patients in each level will be presented by treatment group.

2.4.3 Extent of investigational medicinal product exposure and compliance

The extent of IMP exposure and compliance will be assessed and summarized by actual treatment received within the safety population. (Section 2.3.2).

2.4.3.1 Basal insulin dose

Descriptive statistics of basal insulin dose (U and U/kg) will be presented including change from baseline, relative, change from baseline and change from previous visit.

For change in daily basal insulin at each visit and at endpoint (Week 12 and Week 24), a determination of the average daily insulin doses is made by using daily doses computed on a weekly basis. At each post-baseline visit, the mean daily basal insulin doses will be calculated as the mean of daily insulin doses collected over the last 7 days before the visit. No minimum number of available doses will be required.

In case of any missed doses, corresponding days should not be taken into account in the determination of the average daily insulin doses. In case of premature discontinuation or use of rescue medication, the average daily dose taken into consideration for a patient is the one measured the week before such event.

2.4.3.2 Extent of investigational medicinal product exposure

The extent of IMP exposure will be assessed by the duration of IMP exposure.

Duration of IMP exposure is defined as last dose date – first dose date + 1 day, regardless of unplanned intermittent discontinuations (see Section 2.5.3 for calculation in case of missing or incomplete data). Duration of IMP exposure will be summarized descriptively as a quantitative variable (number, mean, SD, median, minimum, and maximum).

In addition, duration of treatment exposure will also be summarized categorically by numbers and percentages for each of the following categories and cumulatively according to these categories: up to 4 weeks, >4 to 8 weeks; >8 to 12 weeks; >12 to 16 weeks; >16 to 20 weeks; >20 to 22 weeks; >22 to 23 weeks; >23 to 24 weeks and > 24 weeks.

Additionally, the cumulative duration of treatment exposure will be provided, defined as the sum of the duration of treatment exposure for all patients, and will be expressed in patient years.

2.4.3.3 Compliance

No imputation will be made for patients with missing or incomplete data.

Percentage of compliance for a patient will be defined as the number of days with at least one administration divided by the duration of IMP exposure.

Treatment compliance will be summarized descriptively (N, Mean, SD, Median, Min and Max). The percentage of patients with compliance will be summarized for the classes $\leq 60\%$, >60 and ≤ 80 , >80%.

Cases of overdose (provide definition as per protocol) will constitute-adverse events and will be listed as such. More generally, dosing irregularities will be listed in Section 2.2.1.

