# 9.2.1.3 Dose of IMP

The patients document daily their IMP dose and time or any missed IMP injection in the patient diary.

The following values will be entered in the e-CRF:

- For the first 12 weeks (prior to V14, Week 12) of randomized treatment period:
  - Initial IMP starting dose of IMP
  - All available data on the injection time and doses administered will be entered in the e-CRF, including missed IMP injection
- After the first 12 weeks until the end of the randomized treatment period:
  - Daily dose and time of injection from the week last 3 days prior to each site or phone visit
  - In the case of any change in doses administered, the dose and injection time should be entered in the e-CRF
  - Missed IMP injection
- In case of symptomatic hypoglycemia (if appropriate), the dose and injection time should be entered in the e-CRF
- All available data of IMP dose and injection time on the last 3 days before permanently IMP treatment discontinuation

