# 10.1.2 Open-label randomized treatment period (Week 0 to Week 24)

Patients meeting all inclusion criteria and with no exclusion criteria at the end of the screening period are eligible to be enrolled into the open-label randomized treatment period. The duration of the open-label treatment period is 24 weeks  $\pm 5$  days from baseline visit (V2, Week 0) to the end of treatment visit (V20, Week 24).

Each patient self-administers IMP once daily during the open-label treatment period. The IMP dose will be adjusted according to fasting SMPG values recorded in the glucometer (Section 8.2.4).

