# 11.4.1.2 Compliance

A given administration will be considered noncompliant if the patient did not take the planned dose of treatment as required by the protocol. No imputation will be made for patients with missing or incomplete data.

Treatment compliance percentage will be summarized descriptively (N, Mean, SD, Median, Min, and Max). The percentage of patients with compliance is <80% will be summarized.

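### Does the compliance formula mark fully adherent patients as poor compliers because not every dose is entered in the e-CRF after Week 12?

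*SAP*

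**What the plan says.** SAP 2.4.3.3 sets the compliance percentage as "the number of days with at least one administration divided by the duration of IMP exposure" and adds: "No imputation will be made for patients with missing or incomplete data". It reports descriptive statistics and three classes: up to 60%, above 60% to 80%, and above 80%. The denominator comes from SAP 2.4.3.2: "Duration of IMP exposure is defined as last dose date – first dose date + 1 day, regardless of unplanned intermittent discontinuations".

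Protocol 9.2.1.3 states which dose data reach the e-CRF. For the first 12 weeks: "All available data on the injection time and doses administered will be entered in the e-CRF, including missed IMP injection". After Week 12 there are three kinds of entry:

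- a sample of days, worded as "Daily dose and time of injection from the week last 3 days prior to each site or phone visit";
- dose changes: "In the case of any change in doses administered, the dose and injection time should be entered in the e-CRF";
- missed injections, as a separate item.

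The section also asks for doses around symptomatic hypoglycemia, where appropriate, and for the last three days before permanent discontinuation. Protocol 9.2.1.2.1 has the patient write zero units in the diary while the insulin is not taken. Protocol 10.3.1 has the length of each temporary discontinuation recorded in the e-CRF.

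Protocol 11.4.1.2 uses a single cut-off: "The percentage of patients with compliance is <80% will be summarized".

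**The concern.** The numerator is a count of days on which insulin was given, and the denominator is every calendar day from first to last dose. From Week 12 the e-CRF has no routine dose entry for the days between the sampled periods. The SAP does not say how the numerator is to be built, and it rules out imputation. A programmer might count days that carry a dose entry and let all other days fall out of the numerator.

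The compliance table would then show the data-entry schedule instead of adherence. Many completers in both arms would fall below 80%, and real differences in missed injections would be hard to see. In a treat-to-target non-inferiority trial, readers do look at adherence, because poor adherence in both arms could make the treatments look alike.

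**Working it through.** The documents give no expected compliance figure, so there is none to reproduce. The check is a day count for one completer who never misses an injection.

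**Inputs**

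- Treatment length: 24 weeks, 24 × 7 = 168 days. Protocol 10.1.2 allows ±5 days, so 163 to 173.
- Days with full dose entry: 12 × 7 = 84 (Protocol 9.2.1.3).
- Visits after Week 12: six, by phone at Weeks 14, 18 and 22 and on site at Weeks 16, 20 and 24 (Protocol 10.1.2.2 to 10.1.2.4).
- Sampled days per visit: 3 or 7, because the protocol wording can be read either way.

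**Reading A: count only days with a routine dose entry**

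Score = (84 + 6 × k) / exposure days, where k is the number of sampled days per visit.

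| Exposure days | k = 3 | k = 7 |
|---|---|---|
| 163 | 102/163 = 62.6% | 126/163 = 77.3% |
| 168 | 102/168 = 60.7% | 126/168 = 75.0% |
| 173 | 102/173 = 59.0% | 126/173 = 72.8% |

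The low scores are arithmetically right under this reading, but 75% is not a ceiling. A shorter permitted treatment period gives 77.3%. Dose-change entries add days: with k = 7, nine more give 135/168 = 80.4%, which is in the top class. With k = 3 it takes 33 more to reach the same 135.

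**Reading B: count days on which insulin was given**

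Within the exposure period each day either has an administration or does not. Days without one are entered as missed injections throughout, so:

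days with an administration = exposure days − missed days

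Score = (exposure days − missed days) / exposure days.

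- 0 missed: 168/168 = 100%.
- 17 missed: 151/168 = 89.9%.
- 34 missed: 134/168 = 79.8%.

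This ranks patients by missed injections and does not depend on how many days were sampled.

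**Which reading do the texts support?**

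1. The SAP numerator refers to administrations. It does not ask for a dose record on each day. Reading A adds that condition; Reading B is the same ratio derived from the complementary days.
2. Reading A ignores the missed-injection entries that Protocol 9.2.1.3 requires for the period after Week 12.
3. Scoring a blank day as a day without insulin gives that day a value, which is itself a form of imputation. Subtracting recorded missed days uses collected data and imputes nothing.
4. SAP 2.4.3.1 leaves days with missed doses out of the average daily dose. The SAP thus already expects those days to be identifiable.

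**The case for a change.** The strongest reply is that the subtraction is not written in SAP 2.4.3.3. The SAP gives a rule for missed doses when it averages the insulin dose, but none for compliance. One sentence therefore permits results 25 to 39 percentage points apart for the same patient (100 − 75.0 = 25.0; 100 − 60.7 = 39.3). The sampling phrase in Protocol 9.2.1.3 is garbled. The SAP's three classes also differ from the protocol's single cut-off below 80%, and SAP 1.5 does not list that change.

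These observations are accurate, but they do not establish the error. An unstated derivation step is not a wrong formula, and the natural step, given what is collected, yields the correct value. A rule of exposure days minus recorded missed days would only restate the existing definition. The three classes still show what lies at or below 80% and what lies above it; only a patient at exactly 80% is placed differently. The garbled phrase affects how many days feed the SAP's seven-day dose average, and SAP 2.4.3.1 requires no minimum number of doses for that average. It does not affect compliance under Reading B.

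A further reservation is that subtraction relies on missed injections being reported fully; an unreported miss would raise the score. That limit applies to any diary-based adherence measure. Protocol 8.8.1 reduces it by comparing returned pens with the diary dosing records and by having the monitor check the e-CRF against diary entries, treatment logs and unused kits.

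**Conclusion.** The concern does not hold. Under the SAP's definition and the data the protocol collects, a fully adherent 168-day completer scores 100%, not 60.7% or 75.0%. The lower figures need a rule that only dose entries count, which the SAP does not state and which would set aside the missed-injection records. No SAP class is labelled non-compliant.

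The conclusion rests on two assumptions: that the separate missed-injection item in Protocol 9.2.1.3 covers the whole period after Week 12, as its placement indicates, and that sites complete it.

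The consequence would be limited in any case. Compliance is a descriptive summary in the safety population. It is not a term in the primary model (SAP 2.4.4.1.1) and not among the listed per-protocol criteria (SAP 2.3.1.2). The unstated derivation step and the unclear sampling phrase are points of wording that do not change a result of the trial.
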